# Methods

## *Trial design*

A two-arm, parallel randomized, triple-blinded (volunteers, care provider, and outcome assessor), placebo-controlled trial will be carried out. This trial it will be prospectively registered on clinicaltrials.gov.

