## *Randomization and blinding*

Prior to initiation of the treatment, patients will be randomized into their respective intervention groups: APT™ T3X or placebo. Randomization will be generated by a website (<http://random.org/>) and performed by a participating researcher not involved in the recruitment and evaluation of the volunteers. This researcher will be instructed not to disclose the

randomization codes in the intervention groups to any of the volunteers and to the other researchers involved in the study, until its completion. The intervention bottles will be exactly the same regardless of whether it was APT™ T3X or placebo. Concealed allocation will be achieved through the use of sequentially numbered, sealed, and opaque envelopes.

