### *Interventions*

Volunteers will be instructed to use the intervention, according to the prior randomization, once a day, every day, for 21 days. If the volunteer is health professional, it will be instructed to use the intervention twice a day, every day, for 21 days. Intervention specifications included:

- 1) APT™ T3X: The volunteers will be instructed to use 4 drops of tetracycline hydrochloride 3% (APT™ T3X) applied inside of the nasal channels and inside of nostrils.
- 2) Placebo: The volunteers will be instructed to use 4 drops of a formulation composed of FDA approved inactive ingredients applied inside of the nasal channels and inside of nostrils.

All volunteers will be instructed to record each intervention application and to send to a member of the research team in order to control and ensure the adherence to treatment.

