#### **Secondary outcomes**

The secondary outcomes will be presence of adverse events, number of adverse events and frequency of adverse events measured through self-report. In addition, other virus or bacteria contamination rate will be measured through the rate of how many people will be infected with influenza or pneumonia over the course of the study in each group. All secondary outcomes will be measured 22 days after the randomization i.e., after 21 days of application with APT™ T3X or placebo.

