### *Statistical analysis*

The results obtained will first be tested for normality using the Kolmogorov-Smirnov test. The chi-square test or Fisher's exact test for two independent proportions will be used in the statistical analysis of the primary outcome of this study, the COVID-19 contamination rate and for the secondary outcomes: presence of adverse events and another virus or bacteria contamination rate. For the other secondary outcomes, the number of adverse events and frequency of adverse events, the Wilcoxon test will be used if this outcome does not present a normal distribution. If this outcome presents a normal distribution, the two-tailed, unpaired t test will be used. The level of significance used will be 5% ( $p < 0.05$ ).

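### Adverse events are self-reported at Day 22 with no collection period or earlier route described, so counts may rest on up to 21 days' recall; a daily line in the application record would avoid this

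*Combined protocol and SAP*

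**What the plan says.** The Secondary outcomes section names the safety outcomes and their source together: "The secondary outcomes will be presence of adverse events, number of adverse events and frequency of adverse events measured through self-report". Its last sentence fixes the timing: "All secondary outcomes will be measured 22 days after the randomization i.e., after 21 days of application". For the other secondary outcome the same section does state a period, namely "how many people will be infected with influenza or pneumonia over the course of the study in each group". The adverse-event sentence states none.

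The only record described during treatment is in the Interventions section, where volunteers are asked to "record each intervention application and to send to a member of the research team in order to control and ensure the adherence to treatment". The stated purpose is adherence. Adverse events are not mentioned, and the section does not say how often the record is sent.

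The Statistical analysis section tests presence by chi-square or Fisher's exact test. For the counts it says: "For the other secondary outcomes, the number of adverse events and frequency of adverse events, the Wilcoxon test will be used" (if not normally distributed; otherwise an unpaired t test). On blinding, the Trial design section describes a "triple-blinded (volunteers, care provider, and outcome assessor), placebo-controlled trial will be carried out", and Randomization and blinding adds: "The intervention bottles will be exactly the same regardless of whether it was" active or placebo.

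**The concern.** Three of the four secondary outcomes are adverse-event measures, and all three depend on how completely events are captured. The plan gives one method and one time point. If it is followed literally, a volunteer is asked on Day 22 about everything since the first application. Mild, short-lived nasal events early in treatment are the kind that may be forgotten.

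Forgotten events lower the recorded totals and make a real difference between arms harder to see. The Background section says earlier tests of the product were only in vitro, so these self-reports are the tolerability evidence this trial will supply. Events that are not recorded at the time cannot be recovered later.

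**Working it through.** **No plan figure to reproduce.** The document states no adverse-event rate, recall rate or power target. What follows is one piece of date arithmetic and one illustration with assumed inputs.

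**Step 1: recall interval.** Application runs over days 1 to 21 and the report is on day 22. An event on day *d* is recalled over 22 − *d* days: 22 − 1 = 21 for the earliest and 22 − 21 = 1 for the latest. If events were spread evenly over the 21 days, the mean would be (1 + 21)/2 = 11 days. With a daily entry the interval is about one day or less.

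**Step 2: effect on the recorded quantities.** Let each event be recalled independently with probability *r*, and let each affected volunteer have *k* events.
- Mean number recorded = *r* × true mean. It falls 20% at *r* = 0.8 and 50% at *r* = 0.5, whatever *k* is.
- Share of affected volunteers recorded as having any event = 1 − (1 − *r*)^*k*. For *r* = 0.8 this is 0.800, 0.960, 0.992 and for *r* = 0.5 it is 0.500, 0.750, 0.875 (*k* = 1, 2, 3).

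**Step 3: effect on the planned tests.** From the document: 50 per arm and a 5% level. Assumed: two-sided tests throughout (the plan says so only for the t test), 30% vs 10% of volunteers affected, and equal recall in both arms. Fisher and chi-square (no continuity correction) are by full enumeration. Wilcoxon is by simulation with a tie-corrected normal approximation.

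| Events per affected volunteer | Test | Full capture | 80% recall | 50% recall |
|---|---|---|---|---|
| 1 | Presence, Fisher | 64% | 49% | 24% |
| 1 | Presence, chi-square | 73% | 62% | 39% |
| 1 | Number, Wilcoxon | 72% | 60% | 38% |
| 2 | Presence, Fisher | 64% | 61% | 45% |
| 2 | Presence, chi-square | 73% | 71% | 59% |
| 2 | Number, Wilcoxon | 72% | 70% | 57% |
| 3 | Presence, Fisher | 64% | 63% | 55% |
| 3 | Presence, chi-square | 73% | 73% | 67% |
| 3 | Number, Wilcoxon | 72% | 71% | 65% |

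With 40% vs 20% affected and one event each, Fisher power is 52%, 39% and 19%.

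**Step 4: reading the table.** From full capture to 50% recall with two events each, presence by Fisher loses 64 − 45 = 19 points, presence by chi-square 73 − 59 = 14, and number by Wilcoxon 72 − 57 = 15. With one event each the losses are 40, 34 and 34. So although the mean count falls in direct proportion to recall, power for presence can fall as much as, or more than, power for number.

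**The case against.** The strongest objection is that Day 22 is an endpoint time, not a data-collection method. The Primary outcome section uses the same timing for infections accumulated during the study, and volunteers are already sending records to the team. A reader might infer that the plan specifies a single recall interview on Day 22; the text does not say that, and the cumulative reading is natural. What stands is narrower: under either reading, no period for adverse events and no way of collecting them before Day 22 are described.

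Three other stronger readings also go too far.

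- **Bias between arms.** One might infer that recall error will distort the comparison. Volunteers and assessors are blinded and the bottles are identical, so similar recall is plausible. The reverse claim, that bias is ruled out, is not supported either: the placebo is described only as inactive ingredients, with nothing on matching smell or nasal sensation.
- **Harm mainly to number and frequency.** This is true of the mean count, but not of power under the planned tests, as Step 4 shows.
- **A missed power target.** The plan sets none for adverse events, so no stated target is breached.

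It is also fair to say that the illustration does not show the problem is large here. It runs from almost no loss (64% to 63%) to a severe one (64% to 24%), wholly on assumed inputs. Finally, the plan does not say how number differs from frequency. That is a separate gap in definition, which daily collection would not cure, and this point does not rest on it.

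**Conclusion.** The point holds as an improvement worth considering, not as an error in the analysis. The period and the earlier collection route for adverse events are undescribed, and as written the three adverse-event outcomes may rest on recall of up to 21 days. The expected consequence is under-counting and reduced sensitivity in all three.

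The size cannot be determined from the document. The loss is large only if recall is poor and events per volunteer are few; it is small if recall is good, or if recall is fairly good and events repeat. That conclusion assumes independent recall of each event and equal recall in the two arms. Confidence is medium, chiefly because the Day-22 wording can also be read as a cut-off.

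**What to change.** 1. Add one adverse-event entry per calendar day to the application record in the Interventions section: any event, yes or no; if yes, type, start date, and stop date or ongoing. One entry per day, rather than per application, keeps the task the same for health professionals, for whom the plan says: "If the volunteer is health professional, it will be instructed to use the intervention twice a day, every day, for 21 days".
2. State that the record is sent to the team during the 21 days, and how often.
3. In Secondary outcomes, define the adverse-event outcomes as events from first application through Day 22.
4. Keep the Day-22 self-report, and use it to add events not already recorded.

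**Cost.** About 100 × 21 = 2,100 short entries, most of them probably a single no; some reconciliation of the daily record with the Day-22 report; and more minor events recorded in both arms. The sample size, treatment schedule and planned tests do not change.

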### *Statistical analysis*

The results obtained will first be tested for normality using the Kolmogorov-Smirnov test. The chi-square test or Fisher's exact test for two independent proportions will be used in the statistical analysis of the primary outcome of this study, the COVID-19 contamination rate and for the secondary outcomes: presence of adverse events and another virus or bacteria contamination rate. For the other secondary outcomes, the number of adverse events and frequency of adverse events, the Wilcoxon test will be used if this outcome does not present a normal distribution. If this outcome presents a normal distribution, the two-tailed, unpaired t test will be used. The level of significance used will be 5% ( $p < 0.05$ ).

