## *Volunteers and recruitment*

One hundred volunteers will be included in the trial (fifty volunteers per group). The inclusion criteria will be: over 18 years; good general health (without serious health problems); tested negative, by means of immunoglobulin (Ig) G and IgM serology tests and chain real-time polymerase chain reaction (RT-PCR), for COVID-19. The exclusion criteria will be: previous immunization against COVID-19; allergy to tetracycline hydrochloride; diagnosis of Lyme disease; immunocompromised; share housing with someone diagnosed with COVID-19 at the time of the baseline evaluation; serious illnesses, such as cancer, kidney failure, decompensated cardiorespiratory and metabolic diseases, etc.

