### *Outcomes*

#### **Primary outcome**

The primary outcome measured will be the rate of contamination by COVID-19 measured through the rate of how many people will be infected with COVID-19 over the course of the study in each group. This outcome will be measured 22 days after the randomization i.e., after 21 days of application with APT™ T3X or placebo.

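### Does leaving the primary test as chi-square or Fisher, with no correction or interval specified, call for a change to the plan?

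*Combined protocol and SAP*

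**What the plan says.** The primary outcome is binary, "the rate of how many people will be infected with COVID-19 over the course of the study in each group", and the Primary outcome section adds that "This outcome will be measured 22 days after the randomization". The Volunteers and recruitment section sets 100 volunteers, 50 per group. For this outcome the Statistical analysis section then says "The chi-square test or Fisher's exact test for two independent proportions will be used", at a 5% significance level.

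No expected-count threshold is given and the continuity correction is not mentioned. Sidedness is stated only for a secondary analysis of adverse-event counts, where "the two-tailed, unpaired t test will be used". No between-group effect measure or confidence interval is named anywhere.

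**The concern.** A primary analysis should lead every analyst who follows the plan to the same p-value. Here two tests are listed, and one of them has two common forms. With 50 per arm and 22 days of follow-up, infection counts may be small, and that is where these tests differ most. Two analysts could both follow the plan and report opposite conclusions, or one could pick the test after seeing the data. A plan that names only a test also leaves open how the size of the effect will be reported. That matters most for a null result: 5/50 versus 3/50 gives Fisher p = 0.715, but a risk difference of 4.0 points with a Newcombe 95% interval from -7.7 to 16.0.

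**Working it through.** **Inputs.** From the documents: 50 per arm, a binary outcome and a 5% level. Assumed, because the documents give no figures: a two-sided test, infection rates of 10% vs 2%, 15% vs 3%, 15% vs 5% and 20% vs 5%, and the expected-count threshold of 5. The plan states no power or target effect, so there is no figure of its own to reproduce.

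**A borderline table, 9/50 vs 2/50.**
- Uncorrected chi-square = N(ad - bc)² / (product of margins) = 100 × (9×48 - 41×2)² / (50×50×11×89) = 100 × 350² / 2,447,500 = 5.005, p = 0.025.
- Yates: replace 350 by 350 - 50 = 300, giving 100 × 300² / 2,447,500 = 3.677, p = 0.055.
- Fisher, two-sided: p = 0.051.
- Smallest expected count: 50 × 11/100 = 5.5. The usual convention therefore selects chi-square, and only the correction is in doubt.

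By contrast, 7/50 vs 1/50 has a smallest expected count of 50 × 8/100 = 4.0. The convention selects Fisher (p = 0.059), and the uncorrected 0.027 does not arise.

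**How often the verdict changes, 50 per arm.** All tables were enumerated and weighted by binomial probabilities. No table has Fisher rejecting when uncorrected chi-square does not, so the chance that the two disagree is the difference in power.

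| Assumed rates | Power, uncorrected chi-square | Power, Fisher | Disagreement if the tests are interchangeable | Disagreement under the convention, correction open |
|---|---|---|---|---|
| 10% vs 2% | 38.3% | 19.0% | 19% | 1.9% |
| 15% vs 3% | 57.9% | 40.3% | 18% | 8.5% |
| 15% vs 5% | 39.3% | 24.4% | 15% | 10.4% |
| 20% vs 5% | 66.4% | 50.8% | 16% | 13.5% |

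At 10% vs 2% the smallest expected count is below 5 in 92.5% of trials, so the convention nearly always gives Fisher and little is left open. With one participant lost from the higher-rate arm (49 vs 50), the last column becomes 0.7%, 4.5%, 6.2% and 10.4%. Over all splits of 45 to 50 per arm it runs from 0.04% to 13.5%.

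**Type I error.** At common rates of 5%, 10%, 15% and 20% with 50 per arm, uncorrected chi-square has true size 4.3%, 5.1%, 5.5% and 5.2%. Fisher and Yates both have 0.7%, 1.8%, 2.4% and 2.8%. The maximum for uncorrected chi-square is 5.7% at 50 per arm, and 6.1% over the splits of 45 to 50 (reached at 49 vs 49). Since chi-square rejects whenever Fisher does, an analyst who always took the more favourable of the two would have exactly these error rates.

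**The alternative test.** Boschloo's test at 50 per arm has maximum size 4.87% and power 30.4%, 51.2%, 32.1% and 58.3% in the four scenarios. That is above Fisher throughout. Against uncorrected chi-square it loses 38.3 - 30.4 = 7.9, 57.9 - 51.2 = 6.7, 39.3 - 32.1 = 7.2 and 66.4 - 58.3 = 8.1 points.

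**The case for a change.** The best case for a change is that the convention is not written down and would not settle everything if it were. At 8/50 vs 2/50 the smallest expected count is exactly 5, so chi-square applies, and p is 0.046 uncorrected but 0.096 with Yates. The same split occurs at 9 vs 2, 10 vs 3 and 12 vs 4. A single lost participant can also move the conflict: at 9/49 vs 2/50, Fisher falls to 0.028 while Yates stays at 0.0506. Naming a test costs one sentence, and the choice affects power as well as borderline verdicts.

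The omissions are real, and the correction does stay open under the convention. What does not stand is treating the listed tests as freely interchangeable. The same section makes the choice between the t test and the Wilcoxon test depend on the data, so a conditional reading of the chi-square and Fisher pair is the natural one. The 15% to 19% disagreement also comes from strong assumed effects. It is 8% at 10% vs 5%, and 2% to 4% when there is no effect.

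Adopting Boschloo with a Newcombe interval would bring its own conflict. The two disagree in up to 12.3% of trials at 49 vs 50 with 10% vs 2%, where the convention leaves 0.7% open. A tie-break rule would then be needed.

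**Conclusion.** No change to the plan is needed. The section leaves out detail that analysts fill by a familiar rule, and each listed test is defensible: Fisher and Yates are conservative, and uncorrected chi-square stays close to 5% (at most 5.7% at 50 per arm, 6.1% at 49 vs 49). What remains is the continuity correction, which decides about 2% to 14% of trials at 50 per arm under the assumed effects. Choosing among the tests trades power against strict control of size, and Boschloo's test is one more position on that trade-off.

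The outcome is defined as a rate in each group, so both proportions will be reported and a risk difference with its interval follows from the counts. Stating the selection rule, the correction, two-sidedness and an interval method before unblinding would be good housekeeping, but it would not correct an error. The figures rest on assumed infection rates, two-sided testing, an expected-count threshold of 5 and 45 to 50 evaluable participants per arm.

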The topical formulation APT™ Tetracycline 3% formulation (APT™ T3X), is a FDA registered, non-prescription product. This formulation is used in an off-label manner as an intranasal application for prevention of COVID-19 and other viruses. The APT™ T3X as a topical application will penetrate through and into the mucus layer and deeper. This barrier of coverage will provide a mitigation effect to decrease the viral load of exposure and infection. The efficacy of APT™ T3X is due to disrupting the lipid envelope in seconds, hence neutralizing the virus. Previous tests were performed with APT™ T3X and the results found were promising. However, these tests were performed only *in vitro* and clinical studies demonstrating the ability of the APT™ T3X to decrease viral exposure and contamination by COVID-19 are necessary to confirm the possible prophylactic effect, allowing the formulation to be widely distributed to the general population.

Therefore, the aim of this project will be to evaluate the efficacy of the APT™ T3X compared to placebo to decrease COVID-19 contamination rate in humans.

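### Adverse events are analysed only by difference tests at p<0.05 with 50 per arm; no effect estimate or confidence interval is planned, so the analysis cannot say how large an excess of harm is ruled out.

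*Combined protocol and SAP*

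**What the plan says.** The Secondary outcomes section lists "presence of adverse events, number of adverse events and frequency of adverse events measured through self-report", assessed 22 days after randomization. These are the only safety outcomes in the document.

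The Statistical analysis section handles them in two ways. Presence of adverse events shares the primary outcome's method, for which the chi-square or Fisher's "exact test for two independent proportions will be used in the statistical analysis of the primary outcome of this study"; the same sentence extends it "for the secondary outcomes: presence of adverse events and another virus or bacteria contamination rate". For the other two, "the number of adverse events and frequency of adverse events, the Wilcoxon test will be used" if the data are not normal; if they are, "the two-tailed, unpaired t test will be used". One threshold covers everything: "The level of significance used will be 5" per cent.

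The size of the trial is in Volunteers and recruitment: "One hundred volunteers will be included in the trial (fifty volunteers per group". No power statement, expected adverse-event rate, effect estimate or confidence interval appears anywhere, and no sentence says how a non-significant adverse-event result is to be interpreted.

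**The concern.** A difference test asks whether the data are surprising if the two arms have the same risk. The useful safety question is how large an excess of adverse events the trial can exclude. The two answers come apart most in a small trial, where a p-value above 0.05 can sit beside an interval that still includes a large excess.

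The setting makes the second question relevant. Participants are in good general health, the product is a prophylactic, Background and aim says that earlier testing was in vitro only, and the same section looks ahead to "allowing the formulation to be widely distributed to the general population". If the plan is followed exactly, the adverse-event results will consist of p-values. A reader who wants to know how much harm remains possible will find no planned figure.

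**Working it through.** **Inputs from the documents.** 50 per arm (Volunteers and recruitment); significance level 0.05, and chi-square or Fisher for presence of adverse events (Statistical analysis). The rule for choosing between chi-square and Fisher is not given, so both are shown.

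**Assumptions.** Two-sided tests throughout (two-tailed is stated only for the t test); no dropout; adverse-event rates as shown below, because the documents give none. There is no power figure in the plan to reproduce.

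**1. Chance of missing a true excess in presence of adverse events.** Let X1 ~ Binomial(50, p1) on APT T3X and X0 ~ Binomial(50, p0) on placebo. Over all 51 × 51 = 2,601 outcomes,

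miss = 1 − Σ P(X1 = a) · P(X0 = b) · 1[p-value(a, b) < 0.05].

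The chi-square is without continuity correction.

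*A tripling:*

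| Placebo | APT T3X | Missed, chi-square | Missed, Fisher |
|---|---|---|---|
| 2% | 6% | 86% | 97% |
| 5% | 15% | 61% | 76% |
| 10% | 30% | 27% | 36% |
| 15% | 45% | 8% | 11% |
| 20% | 60% | 1% | 2% |

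A tripling from 15% or 20% is an excess of 30 or 40 points, so its detection says little about smaller excesses.

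*A 15-point excess:*

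| Placebo | APT T3X | Missed, chi-square | Missed, Fisher |
|---|---|---|---|
| 5% | 20% | 34% | 49% |
| 10% | 25% | 47% | 59% |
| 15% | 30% | 56% | 65% |
| 20% | 35% | 61% | 68% |
| 30% | 45% | 66% | 73% |

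At placebo rates of 15% to 30%, a 15-point excess is missed 56% to 73% of the time. At 5% it is missed less than half the time.

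**2. What an interval would show.** The Newcombe interval for d = p1 − p0 combines the Wilson limits (l, u) of each arm:

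lower = d − √[(p1 − l1)² + (u0 − p0)²]; upper = d + √[(u1 − p1)² + (p0 − l0)²].

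This step needs no assumed true rate, only example counts.

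- *10/50 in each arm.* Wilson limits 0.112 to 0.330. Upper = 0 + √(0.130² + 0.088²) = 0.157. Both tests give p = 1, yet an excess of up to about 16 points is not excluded.
- *8/50 on APT T3X, 3/50 on placebo.* Wilson limits 0.083 to 0.285 and 0.021 to 0.162; d = 0.10. Upper = 0.10 + √(0.125² + 0.039²) = 0.231; lower = 0.10 − √(0.077² + 0.102²) = −0.028. Fisher p = 0.20 and chi-square p = 0.11, with an interval of −3 to +23 points.
- *18/50 against 10/50.* Non-significant by either test, with an upper limit of +32 points.
- *3/50 in each arm.* Upper limit about +11 points.

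**3. An event never seen on APT T3X.** With 0/50, the exact one-sided 95% upper bound solves (1 − p)^50 = 0.05, so p = 1 − 0.05^(1/50) = 0.058, or 5.8%.

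**4. Number and frequency.** The documents give no mean, variance or distribution for these, so the power of the t and Wilcoxon tests cannot be worked out from them. The omission of an estimate and interval applies equally.

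**The case against.** The stated aim is efficacy, and adverse events are secondary. Low power for harm is ordinary in a trial of this size, and reporting an interval adds no power. The remark about wide distribution is tied to confirming a prophylactic effect, not to a safety claim. Counts by arm will exist, and nothing in the plan forbids describing them. All of this stands. It limits the point to an omission in the planned analysis and does not make it a flaw in the design.

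Two stronger readings are tempting, and the documents do not support them.

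- A reader might infer that a non-significant result will be declared safe. No sentence says so; the plan names tests and a threshold and gives no rule of interpretation. What can be said is that it plans no other quantity for a tolerability statement to rest on.
- A reader might take 61% to 76% as a property of this trial, or conclude that real harm will usually be missed. That range holds at one assumed placebo rate, 5%, and its width reflects only the choice of test. For any self-reported event over 21 days of nasal drops, a rate well above 5% cannot be excluded, and from 15% upward a tripling would nearly always be found. Several of the 15-point scenarios above are also missed less than half the time.

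The fix also needs neither a harm margin nor one particular interval method.

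**Conclusion.** The point holds as a gap in the analysis plan: harm is addressed only by difference tests, with no estimate or interval, so the planned output cannot state the largest excess of adverse events that the data exclude.

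Its practical size depends on rates that the documents do not give. For a tripling, the chance of a miss runs from 86–97% at a 2% placebo rate to 1–2% at 20%. The interval examples depend only on the counts observed: upper limits of +11 to +32 points accompanied non-significant results in the four cases shown. These figures assume 50 evaluable volunteers per arm and two-sided testing. The conclusion that an interval is missing needs none of these assumptions.

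**What to change.** In Statistical analysis, change how the adverse-event outcomes are reported:

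1. For presence of adverse events, make the APT T3X minus placebo risk difference with a 95% interval (Newcombe or another standard score method) the main result, and read the upper limit as the largest excess not ruled out.
2. For number and frequency, give the difference in mean events per volunteer with a 95% interval.
3. Keep the p-values as descriptive, and state that p>0.05 will not be reported as absence of harm. Any tolerability statement should quote the upper limit; for an event not seen in 50 APT T3X volunteers, quote the one-sided 95% upper bound of 5.8%.

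The cost is two or three sentences, with no new volunteers, data or procedures. There are two small downsides. The safety statement will look less favourable, because limits at 50 per arm are wide. And the mean difference is a different estimand from the one the rank test addresses, which the text should acknowledge.
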